## 5.5 General Concomitant Medication and Supportive Care Guidelines

Ivosidenib (AG-120) is a substrate and a potential inducer of CYP2B6 and CYP3A4. Co-administration of AG120 with drugs primarily metabolized by CYP2B6 or 3A4 may result in decreased plasma concentrations of the co-administered drug. Therefore, concurrent use of CYP3A4 substrates should be avoided when possible, but when medically necessary, appropriate dose adjustments of the co-administered drug may be necessary. Examples of CYP3A4 substrates with narrow therapeutic index include cyclosporine, everolimus, sirolimus, and tacrolimus. Careful monitoring of drug levels of immunosuppressant agents is required. Careful consideration should be given to whether participants require the use of azoles and quinolones. An appendix E outlines list of strong CYP3A4 inhibitors, CYP3A4 substrates, and inducers.

Concomitant administration with strong CYP3A4 inhibitors is predicted to increase ivosidenib steady-state C max by up to 52% and AUC by up to 90% which may increase the risk of QTc interval prolongation. Treatment with strong CYP3A4 inhibitors is allowed on this study when they are medically necessary and cannot be avoided or substituted with another medication. However dose adjustment will be necessary with strong CYP3A4 inhibitors (listed in Appendix E) are used concurrently. This will be outlined in section 6.4. Additionally, the investigators must monitor for any changes in toxicity or QT interval, as outlined in section 6.5. Monitoring of subjects receiving study treatment with the combination of these drugs is essential. Providers and investigators should evaluate ECG and electrolytes (including potassium, magnesium, and calcium) at least weekly for the first cycle of therapy. Vigilance is particularly important in subjects presenting with nausea, vomiting, or diarrhea.

Intrathecal chemotherapy for the purposes of prophylaxis is allowed. Intrathecal chemotherapy for the purpose of treating active leukemic disease is not allowed.

If treatment pauses are necessary, per guidance below, due to adverse events on study, if and when ivosidenib is held in the midst of a cycle, the cycle day will not change, and once the drug is resumed it will be either on the day that that cycle has progressed to, or if the pause is beyond 28 days of that cycle, the resumption will be called the day 1 of the subsequent cycle.

---

CONFIDENTIAL

### 5.5.1 Prolonged QT Interval

Participants may be at increased risk for the development of QT prolongation when treated with ivosidenib (AG-120) in combination with fluoroquinolones, azole antifungal agents or serotonin (5-HT3) antagonists. Therefore, treating clinicians need to be vigilant and closely monitor participants receiving any of these drugs; this includes regular evaluation of ECG and electrolytes (including potassium, magnesium, and calcium), particularly in subjects presenting with nausea, vomiting, or diarrhea. Participants will need careful monitoring of the QTcF interval. (See section 6.4 for further information.)

### 5.5.2 IDH Differentiation Syndrome

Subjects treated with ivosidenib (AG-120) have developed signs and symptoms of IDH differentiation syndrome. However, this trial will be in the setting of disease remission, and therefore profound differentiation and differentiation syndrome are highly unlikely in this setting. Nevertheless, the clinical features of differentiation syndrome may include some or all of the following: unexplained fever, skin rash, hypoxia, respiratory compromise, interstitial pulmonary infiltrates, pleural and/or pericardial effusion, weight gain, and clinical deterioration. Laboratory features may include an increase in ANC and/or platelets. An increase in mature leukocytes may be observed in the bone marrow aspirate differential if a bone marrow biopsy is conducted during this time. However, no single sign or symptom may be considered *per se* as diagnostic of the syndrome. If IDH differentiation syndrome is suspected, Investigators need to report the suspected diagnosis as an SAE. It is recommended that the prophylactic and therapeutic measures indicated below are undertaken at the earliest manifestations of suspected IDH differentiation syndrome:

- Temporary hold of AG-120 treatment only if symptoms cannot be medically managed with the following:
  - Prompt initiation of hydroxyurea at a suggested dose of 2 to 3 g PO two or three times daily
  - Prompt administration of corticosteroids at a suggested dose 10 mg of dexamethasone IV every 12 hours until disappearance of symptoms and signs, and for a minimum of 3 days
  - Initiation of furosemide, if clinically required
  - Prompt initiation of leukapheresis, if required
  - Immediate communication with the Principal Investigator, [name], is encouraged for guidance regarding treatment. Once the signs and symptoms resolve and the subject's clinical condition improves, AG-120 may be reinitiated if study treatment was withheld. The dose of AG-120 at re-initiation is to be discussed with the Principal Investigator.

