### **6.3 Non-Hematologic Toxicity (except QT prolongation)**

If at any time during ivosidenib dosing, a participant experiences a grade 3 or higher toxicity that is possibly, probably or definitely related to ivosidenib, drug must be held until the toxicity resolves to a grade 1 or lower. If it is during the first cycle (28 days) of dosing, the toxicity will be considered to be a DLT (see section 5.4). In participants with known Gilbert’s disease, grade 3 elevated bilirubin that is possibly, probably or definitely related to ivosidenib would not require study drug hold if the elevation is not due to liver GVHD or veno-occlusive disease. For these participants, study drug must be held for grade 4 elevated bilirubin and resolution/recurrence of toxicity to follow the instructions below in 6.3.1 and 6.3.2.

If and when ivosidenib is held in the midst of a cycle, the cycle day will not change, and once the drug is resumed it will be either on the day that that cycle has progressed to, or if the pause is beyond 28 days of a cycle, the resumption will be called the day 1 of the subsequent cycle.

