### 6.3.2 500 mg dosing

If the participant was at the 500mg daily dosing level when the toxicity occurred, and the toxicity resolves to  $\leq$  grade 1 *after* 14 days, but *before* 28 days (total) have elapsed, then dosing with ivosidenib can resume at the reduced dose of 250 mg daily. If the attributable toxicity recurs at  $\geq$  grade 3 (or grade 4 bilirubinemia in those with known Gilbert's disease – see above section 6.3) during the course of the study, then the participant will come off treatment and will remain on study only for survival and other outcomes.

If the participant was at the 500mg daily dosing level when the toxicity occurred, and it takes *less than* 14 days for the event to resolve to  $\leq$  grade 1, then dosing with ivosidenib can resume at 500mg daily. If the toxicity recurs at  $\geq$  grade 3 (or grade 4 bilirubinemia in those with known Gilbert's disease – see above section 6.3), then dosing will again be held. (This will be a DLT if it occurs during cycle 1). If the toxicity again resolves to  $\leq$  grade 1 within 28 days, then dosing with ivosidenib can resume at the reduced dose of 250mg daily. If the toxicity recurs yet again at  $\geq$  grade 3 (or grade 4 bilirubinemia in those with known Gilbert's disease – see above section 6.3), then the participant will come off treatment and will remain on study only for survival and other outcomes.

A participant who starts at 500mg daily dosing and is subsequently reduced to 250mg daily dosing due to toxicity can potentially increase back up to 500mg daily dosing if subsequent evaluation of the observed toxicity indicates no relation to study drug. Any such re-escalation must have the approval of the principal investigator, [name].

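### For related, grade 3 or higher, medically manageable differentiation syndrome, Sections 5.5.2 and 6.3 give opposite instructions on holding ivosidenib

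*Combined protocol and SAP*

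**What the plan says.** Section 5.5.2 deals with differentiation syndrome by name. Its instructions open as advice: "It is recommended that the prophylactic and therapeutic measures indicated below are undertaken at the earliest manifestations of suspected IDH differentiation syndrome". The first item is "Temporary hold of AG-120 treatment only if symptoms cannot be medically managed with the following", followed by hydroxyurea, corticosteroids, furosemide and leukapheresis. No CTCAE grade appears. If drug was withheld, it may be restarted once signs and symptoms have resolved and the patient has improved. On the dose, the section says: "The dose of AG-120 at re-initiation is to be discussed with the Principal Investigator". No time limit is attached. Every suspected case is to be reported as an SAE.

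Section 6.3 covers non-hematologic toxicity in general. When a toxicity of grade 3 or higher is at least possibly related to ivosidenib, "drug must be held until the toxicity resolves to a grade 1 or lower". The section heading excludes QT prolongation, which has its own rules in 6.5. The only exception in the text is grade 3 bilirubin in known Gilbert's disease, which "would not require study drug hold if the elevation is not due to liver GVHD or veno-occlusive disease".

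Sections 6.3.1 and 6.3.2 then set what follows a hold. At 250 mg, the participant leaves treatment if resolution takes longer than 14 days, and may restart at 250 mg if it takes less. At 500 mg, resolution in less than 14 days allows a return to 500 mg. If resolution comes after 14 but before 28 days, "then dosing with ivosidenib can resume at the reduced dose of 250 mg daily".

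**The concern.** The syndrome as 5.5.2 describes it consists mainly of fever, rash, hypoxia, lung infiltrates, effusions and weight gain. These are non-hematologic, and the section presents them as seen in patients given this drug. A severe case therefore falls within 6.3 as well as 5.5.2. One section confines the hold to cases that supportive treatment cannot control, and the other makes the hold compulsory on grade alone.

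What is at stake is consistent dosing during a serious event in a multicenter trial. A clinician facing the syndrome would naturally turn to the section named for it, while a coordinator checking dose modifications would turn to Section 6. If 6.3 prevails, a site that continues drug under 5.5.2 has departed from a mandatory rule. Appendix B, Section 3.8.2, classes such a departure as a violation unless the IRB approved it beforehand.

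**Working it through.** The plan gives no figure on this point, so the check compares the texts.

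**Step 1. Cases.** Take differentiation syndrome judged at least possibly related to ivosidenib and split it by grade and manageability.

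| Case | Section 5.5.2 | Section 6.3 | Conflict on the hold? |
|---|---|---|---|
| Grade 1-2 | Hold only if not manageable | Not triggered | No |
| Grade 3 or higher, not manageable | Hold | Hold | No |
| Grade 3 or higher, manageable | No hold | Hold to grade 1 or lower | Yes |

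Only the third row is contradictory.

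**Step 2. Does another passage settle the third row?**

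- The exceptions to 6.3 are QT prolongation and bilirubin in Gilbert's disease. Neither concerns differentiation syndrome.
- Section 6.7 applies only to grade 4 neutropenia and thrombocytopenia, so it does not take the syndrome out of 6.3.
- The tie-break at the start of Section 6 applies when more than one adverse event leads to different dose reductions. It does not decide between holding and continuing for one event.
- Section 5.1 sends the reader to Section 6 for dose modifications, and 5.4 does the same for events that meet the DLT definition. Neither says that Section 6 overrides 5.5.2.
- Section 5.5.2 does not refer to 6.3, and the table of contents lists no differentiation-syndrome section within Section 6.

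**Step 3. Restart, if drug is held.**

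| Situation | Section 5.5.2 | Sections 6.3.1 and 6.3.2 |
|---|---|---|
| 250 mg, resolves in under 14 days | May restart; dose by discussion | May restart at 250 mg |
| 250 mg, takes more than 14 days | May restart; dose by discussion | Off treatment |
| 500 mg, resolves in under 14 days | May restart; dose by discussion | May resume at 500 mg |
| 500 mg, resolves after 14 but before 28 days | May restart; dose by discussion | May resume at 250 mg |

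The clearest mismatch is the second row, where one section permits re-initiation and the other ends treatment.

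**Step 4. Effect on DLTs.** Section 5.4 counts a drug-related non-hematologic event of grade 3 or higher as a DLT, excepting only short-lived nausea, vomiting or diarrhea that responds to treatment. Section 6.3 repeats that such a toxicity in the first cycle is a DLT. A third-row event in cycle 1 is therefore a DLT whether drug is held or continued.

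**The case against.** The best counter-argument is that the documents lean toward Section 6. Section 5.5.2 is phrased as a recommendation and 6.3 as an obligation. Section 5.4 refers management of DLT-type events to Section 6, which takes in the cycle 1 conflict case. This is a fair reading, but it remains an inference. None of these pointers is a precedence clause, and the restriction in 5.5.2 on when to hold is explicit.

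On restart, the permissive wording of 6.3.2 can be squared with a discussion with the Principal Investigator, who may simply apply 6.3.2. That largely answers the point at 500 mg. It does not answer it at 250 mg beyond 14 days, where 6.3.1 takes the participant off treatment. Restart is therefore a secondary matter.

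SAE reporting to the Coordinating Center and the Principal Investigator (Section 7.4), and the encouragement in 5.5.2 to contact the latter at once, should limit divergence between sites. They do not tell a site what to do with the drug when the event occurs.

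Three stronger readings are tempting, and the documents do not support them.

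- A reader might infer that every case of the syndrome gets contradictory instructions. Two of the three cases in the first table do not conflict on the hold.
- A reader might infer that the length of a hold changes the DLT count through the clause in 5.4 on taking 75% of doses. The event is already a DLT by grade, so that clause adds nothing. The rule in 5.1 that a participant must receive at least 50% of dosing to be evaluable could matter after a long hold. How that rule fits with the evaluability definition in Section 13 is a separate question, not created by 5.5.2.
- A reader might project the 1-10% band in 7.1.1 onto the planned sample. That band is a shared heading over QT prolongation, differentiation syndrome and leukocytosis, with no grade given. It says nothing about the grade 3 or higher, manageable subset.

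**Conclusion.** The point holds in limited form, and the text is wrong as written rather than short of detail. Two stated safety rules contradict each other on the hold for differentiation syndrome that is at least possibly related, grade 3 or higher and medically manageable. The restart rules are also not aligned, most clearly at 250 mg when resolution takes more than 14 days.

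The consequence is inconsistent dosing across sites during a serious event. The documents do not support a claim of bias in the recommended phase 2 dose, since the DLT count should not usually change. The frequency cannot be given: there is no rate for this subset, and 5.5.2 itself regards the syndrome as very improbable in patients in remission.

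This rests on two assumptions. The first is that the investigator attributes the event at least possibly to ivosidenib, which 6.3 requires. The second is that no exception appears in Section 6.6 (neurologic toxicities), which was not in the copy checked. Its title gives no reason to expect one.

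**What to change.** Reconcile 5.5.2 with 6.3, 6.3.1 and 6.3.2 so that one passage governs both hold and restart for differentiation syndrome, and cross-reference it from the other. There are two ways to do this in wording: name the syndrome as an exception to 6.3, as is done for QT prolongation, or state in 5.5.2 that the grade-based rules of 6.3 to 6.3.2 apply. Which rule should govern is a clinical decision for the investigators, and this review takes no position on it.

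The cost is a wording amendment and a clarification letter to sites. No procedures, visits or participants are added.

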### 5.5.3 Leukocytosis

Ivosidenib/AG-120 may be associated with leukocytosis that can occur without progression of AML. It is recommended that the prophylactic and therapeutic measures indicated below be

CONFIDENTIAL

This document is confidential. Do not disclose or use except as authorized.

undertaken at the earliest manifestations of leukocytosis:

- Temporary hold of study treatment only if symptoms cannot be medically managed with the following:
  - Prompt initiation of hydroxyurea at up to a dose of 2000 or 3000 mg PO BID
  - Prompt initiation of leukapheresis, if required

Treatment with hydroxyurea is allowed after the start of AG-120 for initial control of peripheral leukemic blasts in subjects with leukocytosis (for example, WBC >30,000/ $\mu$ L) during the course of AG-120 therapy with approval of the Principal Investigator.

Immediate communication with the Principal Investigator is encouraged for guidance regarding treatment. Once the signs and symptoms resolve and the subject's clinical condition improves, AG-120 may be reinitiated if study treatment was held. If it was held, then the dose of AG-120 at reinitiation is to be discussed with the Principal Investigator.

## **5.6 Criteria for Taking a Participant Off Therapy**

Participants with persistent remission can continue receiving ivosidenib for 12 cycles.

Duration of therapy will depend on tolerance and evidence of disease progression. In the absence of treatment delays due to adverse event(s), treatment may continue for 12 cycles or until one of the following criteria applies:

- Disease progression
- Intercurrent illness that prevents further administration of treatment
- Unacceptable adverse event(s)
- Participant demonstrates an inability or unwillingness to comply with the oral medication regimen and/or documentation requirements
- Participant decides to withdraw from the protocol therapy
- General or specific changes in the participant's condition render the participant unacceptable for further treatment in the judgment of the treating investigator

Participants will be removed from protocol therapy when any of these criteria apply. Alternative care options will be discussed with the participant. The reason for removal from protocol therapy, and the date the participant was removed, must be documented in the case report form (CRF). The DF/HCC research team will update the relevant Off Treatment/Off Study information in the CTMS, OnCore. The Coordinating Center will update this information for external site participants.

## **5.7 Duration of Follow Up**

Participants will be followed for 24 months from the start of protocol therapy or until death, whichever occurs first. Participants removed from protocol therapy for unacceptable adverse event(s) will be followed until resolution or stabilization of the adverse event. Participants who

---

CONFIDENTIAL

This document is confidential. Do not disclose or use except as authorized.

conclude or are removed from protocol treatment and begin a new therapy will be followed for survival only. Adverse event and toxicity data will not be collected for patients who initiate new therapy. Follow-up assessments for study purposes will occur every 3 months per the study calendar in Section 10.

## **5.8 Criteria for Taking a Participant Off Study**

Participants will be removed from study when any of the following criteria applies:

- Lost to follow-up
- Withdrawal of consent for data submission
- Death

The reason for taking a participant off study, and the date the participant was removed, must be documented in the case report form (CRF). The DF/HCC research team will update the relevant Off Treatment/Off Study information in the CTMS, OnCore in accordance with DF/HCC policy REGIST-101. The Coordinating Center will update this information for external site participants.

## **6. DOSING DELAYS/DOSE MODIFICATIONS**

Dose delays and modifications will be made as indicated below. The descriptions and grading scales found in the revised NCI Common Terminology Criteria for Adverse Events (CTCAE) version 4.03 will be utilized for dose delays and dose modifications. A copy of the CTCAE version 4.03 can be downloaded from the CTEP website

[http://ctep.cancer.gov/protocolDevelopment/electronic\\_applications/ctc.htm](http://ctep.cancer.gov/protocolDevelopment/electronic_applications/ctc.htm).

If a participant experiences several adverse events and there are conflicting dose reduction recommendations, the dose should be adjusted to the lowest recommended level.

Regarding pauses in dosing due to adverse events on study, if and when ivosidenib is held in the midst of a cycle, the cycle day will not change, and once the drug is resumed it will be either on the day that that cycle has progressed to, or if the pause is beyond 28 days of a cycle, the resumption will be called the day 1 of the subsequent cycle.

### **6.1 Acute GVHD**

As mentioned previously, acute GVHD prior to study entry must be clinically stable and requiring  $\leq 0.5$  mg/kg/day of prednisone. For patients who initiate therapy and develop new onset acute GVHD:

- Therapy with topical / local agents such as corticosteroid / tacrolimus cream, oral non-absorbable steroids, ursodiol, etc. are allowed to be used and ivosidenib will continue. Discussion with the Principal Investigator is encouraged.

---

CONFIDENTIAL

This document is confidential. Do not disclose or use except as authorized.

- Systemic therapy  $\leq 0.5$  mg/kg/day of prednisone is allowed to be used with continuation of ivosidenib – i.e. starting 20 mg / day for presumed upper GI GVHD. In no way is this study advocating for the use of a specific dose of steroids for initial therapy of acute GVHD, and treatment of such should not be compromised to continue ivosidenib.
- If requiring systemic steroids  $> 0.5$  mg/kg/day of prednisone, ivosidenib will be held and initial therapy for acute GVHD initiated. If within the next 28 days, the participant is able to improve and be on a stable dose of steroids which is  $\leq 0.5$  mg/kg/day of prednisone (or equivalent), ivosidenib may be restarted at the original dose.
- Participants are forbidden from receiving any “investigational” agents for the treatment of acute GVHD. Discussion with the overall PI is encouraged to define “investigational.” Patients are allowed to participate on clinical trials investigating initial therapy for acute GVHD – i.e. using agents with steroids or agents alone which are not “investigational.”
- If acute GVHD occurs in the dose-escalation cohorts, and this occurs during the first cycle of treatment and patient has taken  $< 14$  days of drug, the participant may be replaced, as DLT evaluation would be impacted.
- Any initiation of systemic therapy beyond steroids for steroid-refractory acute GVHD will result in the participant stopping ivosidenib. Systemic therapy beyond steroids for participants with *steroid-dependent* acute GVHD is allowed and will not result in participant stopping ivosidenib. Discussion with the PI is encouraged.
- For flares of acute GVHD, participants are allowed to increase systemic steroid dose, however, if exceeding 0.5 mg/kg/day of prednisone or equivalent, ivosidenib will be held and the patient will have 28 days to restart if symptoms and steroid requirement guidelines can be met.

